7.2 Exclusion Criteria

Any subject who meets any of the following criteria will not qualify for entry into the study:

1. The subject has received any investigational compound within 30 days prior to the first dose of study drug.
2. The subject has received TAK-071 in a previous clinical study.
3. The subject is an immediate family member, study site employee, or is in a dependent relationship with a study site employee who is involved in the conduct of this study (eg, spouse, parent, child, sibling) or may consent under duress.
4. The subject has uncontrolled, clinically significant neurologic, cardiovascular, pulmonary, hepatic, renal, metabolic, gastrointestinal, or endocrine disease or other abnormality (other than the disease being studied), which may impact the ability of the subject to participate or potentially confound the study results.
5. The subject has a known hypersensitivity to any component of the formulation of TAK-071 or placebo; or has a known hypersensitivity to donepezil (or to other biperidine derivatives), atropine, or scopolamine and/or to any component in their formulations.
6. The subject has a positive urine drug result for drugs of abuse (defined as any illicit drug use) at Screening or Check-in (Day -1) of Period 1.

7. The subject has a history of drug abuse (defined as any illicit drug use) or a history of alcohol abuse (defined as regular consumption of 4 or more units per day) within 1 year prior to the Screening visit or is unwilling to agree to abstain from alcohol and drugs throughout the study. One unit is equivalent to a half-pint of beer or 1 measure of spirits or 1 glass of wine.
8. Subject has taken any excluded medication, supplements, or food products during the time periods listed in the Excluded Medications and Dietary Products table listed in Section 7.4.
9. Subject intends to donate sperm during the course of this study or for 70 days after the last dose of study drug.
10. There is any finding in the subject's medical history, physical examination, or safety laboratory tests giving reasonable suspicion of a disease that would contraindicate taking TAK-071, donepezil, scopolamine, or a similar drug in the same class, or that might interfere with the conduct of the study.
11. Subject has current or recent (within 6 months) gastrointestinal disease that would be expected to influence the absorption of drugs (ie, a history of malabsorption, esophageal reflux, peptic ulcer disease, erosive esophagitis, frequent [more than once per week] occurrence of heartburn, or any surgical intervention).
12. Subject has a history of cancer, except basal cell carcinoma which has been in remission for at least 5 years prior to Day 1 of Period 1.
13. Subject has a positive test result for hepatitis B surface antigen (HBsAg), hepatitis C virus (HCV) antibody at Screening or a known history of human immunodeficiency virus infection.
14. Subject has used nicotine-containing products (including but not limited to cigarettes, pipes, cigars, chewing tobacco, nicotine patch or nicotine gum) within 28 days prior to Check-in Day -1 of Period 1. Cotinine test is positive at Screening or Check-in (Day -1) of Period 1.
15. The subject has poor peripheral venous access.
16. Subject has donated or lost 450 mL or more of his blood volume (including plasmapheresis), or had a transfusion of any blood product within 30 days prior to Day 1 of Period 1.
17. The subject has a risk of suicide or suicidal ideation with intent and plan according to the investigator's clinical judgment (affirmative answer to questions 4 and 5 of the ideation section of the Columbia-Suicide Severity Rating Scale [C-SSRS]) or has made a suicide attempt in the previous 6 months.
18. The subject is a shift worker (night, late, or early resulting in irregular bed times) or has crossed or will cross more than 2 time zones within 48 hours in the period from 48 hours prior to Treatment Period 1, Day 1 until the end of Treatment Period 5.
19. The subject reports symptoms suggesting evidence of a current sleep disorder or history of sleep disorder, including but not limited to sleep apnea, heavy snoring, primary or chronic insomnia, narcolepsy or restless leg syndrome, as judged by medical history.

20. The subject has a Fridericia-corrected QT interval >450 ms or PR interval outside the range of 120 to 220 ms, confirmed on repeat testing within a maximum of 30 minutes, at Screening or Check-in.
21. Subject has abnormal Screening or Check-in (Day -1) of Period 1 laboratory values that suggest a clinically significant underlying disease, confirmed upon repeat testing.

7.3 Additional Inclusion Criteria for Part 2 After Pre-Enrollment Enrichment Screening

1. Subject able to perform the CogState battery.
2. Change from Baseline (average) in total GMLT errors of ≤ -5 at 2 hours postdose of scopolamine.
3. Subjects with sleepiness score <8 on the KSS at 2 hours postdose of scopolamine.
4. Subject passes a hearing test with at least 80% correct responses and no more than 20% false positives. This test can be repeated once to determine eligibility.

7.4 Excluded Medications, Supplements, Dietary Products

Use of the agents in [Table 7.a](#) is prohibited from the time points specified until subject completes PK assessment on Day 8 in Part 1, the initial substudy, or is discharged from the unit in Period 5 in Part 2, the main study.

Table 7.a Prohibited Medications, Supplements, Dietary Products

28 Days Prior to Check-in (Day -1) of Period 1	7 Days Prior to Check-in (Day -1) of Period 1	72 Hours Prior to Check-in (Day -1) of Period 1
Prescription medications (other than donepezil, where applicable)	OTC medications (a)	Products containing caffeine
Nutraceuticals (eg, St. John's wort, ginseng, kava kava, ginkgo biloba, Chinese herbs, and melatonin)	Vitamin supplements	poppy seeds
Intake of known OTC inhibitors/inducers of CYPs 3A4/5, 2C9, 2C19, 2D6, 1A2, 2B6, 2E1, and 2A6 (b) Intake of the following drug classes: anti-emetics; antidiarrhetics, anticholinergics, cholinergic agonists and laxatives	Foods or beverages containing grapefruit or Seville-type (sour) oranges and marmalade, apple, orange, or pineapple juices, vegetables from the mustard green family (eg, kale, broccoli, watercress, collard greens, kohlrabi, Brussels sprouts, mustard), and charbroiled meats	
Nicotine-containing products	Alcohol containing products	
Immunization/vaccines		

OTC=over-the-counter.

(a) Occasional use of acetaminophen/paracetamol (≤ 1 g/day) or other medication as approved by Takeda on a case-by-case basis is allowed, but is prohibited on dosing and sample collection days. Prohibition and approval on a case-by-case basis may both be acceptable terms.

(b) For a list of moderate/strong CYP3A4, 2D6, or 2C9 inducers/inhibitors, see [Appendix F](#).

Subjects must be instructed not to take any medications including OTC products, without first consulting with the investigator.

7.5 Diet, Fluid, and Activity Control

7.5.1 Part 1

Subjects will be confined to the clinic for the duration of the treatment period (Day -1 through Day 4).

During the confinement period, subjects will receive 3 meals and an evening snack. The breakfast on Day 1 will be a low-fat, low-calorie, defined as <300 calories and <20% fat content. The 2 meals will have approximately 30% fat (relative to the total calories). The study menu should be recorded and submitted to the study file with a copy provided to the sponsor prior to the start of the study. The start and end time of meals and percentage of meals consumed on Days 1 to 2 will be recorded in the electronic case report form (eCRF).

7.5.2 Part 2

Subjects will be confined to the clinic for the duration of each treatment period (Day -1 through Day 3).

During the confinement in each treatment period, subjects will receive 3 meals and an evening snack. The breakfast on Day 1 of each treatment period will be a low-fat low-calorie, defined as <300 calories and <20% fat content. The 2 meals will have approximately 30% fat (relative to the total calories). The meals served on the day of dosing should be identical (same items offered) for each period in the study. The study menu should be recorded and submitted to the study file with a copy provided to the sponsor prior to the start of the study. The start and end time of meals and percentage of meals consumed on Days 1 and 2 will be recorded in the eCRF.

TAK-071 or matching placebo will be administered with approximately 240 mL of water after a fast of at least 8 hours as a single PO dose (DIC) 24 hours before scopolamine dosing and approximately 1.5 hours following a low-calorie, low-fat breakfast. No additional food will be permitted for up to 4 hours after TAK-071 dosing. Donepezil will be administered with approximately 240 mL of water after a fast of at least 8 hours as a single PO dose 3 hours before scopolamine dosing. Subjects may consume water ad libitum with the exception of 1 hour before and 1 hour after TAK-071, donepezil, or placebo administration. Meal timings, as well as their caloric and fat content, may be changed in the event of adjustments to the TAK-071 administration time.

Subjects will remain upright (seated, standing, or ambulatory) for 1 hour following the dose administration, except as necessitated by the occurrence of an AE or study procedures (eg, obtaining 12-lead ECG). Subjects will refrain from strenuous and/or unaccustomed exercise throughout the entire course of the study.

7.6 Criteria for Discontinuation or Withdrawal of a Subject

The primary reason for discontinuation or withdrawal of the subject from the study or study drug should be recorded in the eCRF using the following categories. For screen failure subjects, refer to Section 9.1.18.

1. Pretreatment event (PTE) or AE. The subject has experienced a PTE or AE that requires early termination because continued participation imposes an unacceptable risk to the subject's health or the subject is unwilling to continue because of the PTE or AE.

- Liver function test (LFT) abnormalities

Study drug should be discontinued immediately with appropriate clinical follow-up (including repeat laboratory tests, until a subject's laboratory profile has returned to normal/Baseline status, see Section 9.1.8), if the following circumstances occur at any time during study drug treatment:

- Alanine aminotransferase (ALT) or aspartate aminotransferase (AST) >8× upper limit of normal (ULN), or
- ALT or AST >5× ULN and persists for more than 2 weeks, or
- ALT or AST >3× ULN in conjunction with elevated total bilirubin >2× ULN or international normalized ratio (INR) >1.5, or

- ALT or AST $>3 \times$ ULN with appearance of fatigue, nausea, vomiting, right upper quadrant pain or tenderness, fever, rash and/or eosinophilia ($>5\%$).
- 2. Significant protocol deviation. The discovery post-randomization that the subject failed to meet protocol entry criteria or did not adhere to protocol requirements, and continued participation poses an unacceptable risk to the subject's health.
- 3. Lost to follow-up. The subject did not return to the clinic and attempts to contact the subject were unsuccessful. Attempts to contact the subject must be documented in the subject's source documentation.
- 4. Voluntary withdrawal. The subject (or subject's legally acceptable representative) wishes to withdraw from the study. The reason for withdrawal, if provided, should be recorded in the eCRF.

Note: All attempts should be made to determine the underlying reason for the withdrawal and, where possible, the primary underlying reason should be recorded (ie, withdrawal due to an AE should not be recorded in the "voluntary withdrawal" category).

- 5. Study termination. The sponsor, IRB, independent ethics committee (IEC), or regulatory agency terminates the study.
- 6. Other.

Note: The specific reasons should be recorded in the "specify" field of the eCRF.

7.7 Procedures for Discontinuation or Withdrawal of a Subject

The investigator may discontinue a subject's study participation at any time during the study when the subject meets the study termination criteria described in Section 7.6. In addition, a subject may discontinue his or her participation without giving a reason at any time during the study. Should a subject's participation be discontinued, the primary criterion for termination must be recorded by the investigator. In addition, efforts should be made to perform all procedures scheduled for the Early Termination Visit. Discontinued or withdrawn subjects will not be replaced.

8.0 CLINICAL STUDY MATERIAL MANAGEMENT

This section contains information regarding all medications and materials provided directly by the sponsor, and/or sourced by other means, that are required by the study protocol, including important sections describing the management of study material.

8.1 Study Drug

8.1.1 Dosage Form, Manufacturing, Packaging, and Labeling

In this protocol, the term “study drug” refers to all or any of the drugs defined below.

- TAK-071 and matching placebo.
- Scopolamine and matching placebo.
- Donepezil and matching placebo.

8.1.1.1 *Investigational Study Drug*

TAK-071 Drug Substance

TAK-071 drug substance will be manufactured by Ube Industries Limited, Yamaguchi, Japan and supplied to the clinical site and then compounded into a hard capsule.

TAK-071 DIC and Matching Placebo

The TAK-071 DIC will be prepared at the clinical site by feeding TAK-071 drug substance into a hard gelatin capsule (color: Swedish orange opaque). The range of TAK-071 drug substance loaded will be 1 to 30 mg per capsule. Compounding and blinding instructions will be provided to the clinical site using the compounding worksheet or a similar document. The matching placebo will be an empty capsule and will also be prepared at the site.

The composition of the TAK-071 DIC and matching placebo is provided in [Table 8.a](#).

Table 8.a Composition of TAK-071 for DIC and Matching Placebo

Components	TAK-071 DIC	Matching Placebo
TAK-071	1-30 mg	0 mg
Hard gelatin capsule (Size: 00, Color: Swedish orange opaque)		

8.1.1.2 *Donepezil and Matching Placebo*

Donepezil 10 mg tablet manufactured by Eisai Inc. will be overencapsulated, labeled in a blinded fashion with third-party dispensing, and delivered as a PO capsule. The composition of the overencapsulated donepezil and matching placebo is provided in [Table 8.b](#).

Table 8.b Composition of Overencapsulated Donepezil and Matching Placebo

Components	Aricept OE	Matching Placebo
Donepezil 10 mg tablet, United States Pharmacopeia	1 tablet	-
Microcrystalline cellulose, National Formulary	qs	qs
Hard gelatin capsule (Color: Swedish orange opaque)		

OE=overencapsulated.

qs=quantity sufficient.

8.1.1.3 *Scopolamine and Matching Placebo*

Scopolamine, under generic name hyoscine hydrobromide, manufactured by Martindale Pharmaceuticals Ltd. will be delivered as a 0.5 mg SC injection.

The placebo for scopolamine will be the equivalent volume of saline delivered as SC injection.

8.1.1.4 *Sponsor-Supplied Drug*

TAK-071 drug substance is manufactured by Ube Industries Limited, Yamaguchi, Japan and supplied to the clinical site by Takeda Development Center Americas, Inc. (TDC Americas).

Scopolamine will be sourced from the United Kingdom as hyoscine hydrobromide 600 µg/mL ampoules and supplied to the clinical site by TDC Americas.

Branded Aricept (as donepezil) will be sourced locally and overencapsulated by the clinical site.

8.1.2 **Storage**

Based upon the recent stability study data, the recommended storage conditions for the TAK-071 DIC are 20°C to 25°C (68°F to 77°F), with excursion permitted within 15°C to 30°C (59°F to 86°F). Any excursions from the labeled storage conditions must be reported to Takeda immediately.

Overencapsulated donepezil must be stored according to the label.

Scopolamine must be stored according to the commercial label.

All clinical trial material must be kept in an appropriate, limited-access, secure place until it is used or returned to the sponsor or designee for destruction.

All study drugs must be stored under the conditions specified on the label and remain in the original container until dispensed. A daily temperature log of the drug storage area must be maintained every working day.

8.1.3 **Dose and Regimen**

8.1.3.1 *Part 1*

TAK-071 80 mg on Day 1 (24 hours prior to scopolamine administration) administered as DIC PO and scopolamine 0.5 mg SC on Day 2.

8.1.3.2 Part 2

TAK-071 dose will be selected based on the SRD part of the study TAK-071-1001 and part 1 of this study.

- Treatment A=scopolamine matching placebo SC + TAK-071 matching placebo PO + donepezil matching placebo PO.
- Treatment B=scopolamine 0.5 mg SC + TAK-071 matching placebo PO + donepezil matching placebo PO.
- Treatment C=scopolamine 0.5 mg SC + TAK-071 PO + donepezil matching placebo PO.
- Treatment D=scopolamine 0.5 mg SC + TAK-071 PO + donepezil 10 mg PO.
- Treatment E=scopolamine 0.5 mg SC + TAK-071 matching placebo PO + donepezil 10 mg PO.

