

Primary Objective:
 
 To assess the effect of a single PO dose of TAK-071 on the attenuation of cognitive deficit induced by scopolamine (0.5 mg SC) as measured by GMLT (total number of errors). 
Secondary Objectives:
 
 To characterize the safety and tolerability of a single PO dose of TAK-071 when coadministered with SC scopolamine (0.5 mg) in healthy subjects. To characterize the single PO dose plasma PK profile of TAK-071 when coadministered both with scopolamine and a low-calorie, low-fat breakfast in healthy subjects. To demonstrate assay sensitivity by using donepezil 10 mg as the positive control. To assess the effect of a single PO dose of TAK-071 in combination with 10 mg donepezil on the attenuation of cognitive deficit induced by scopolamine (0.5 mg subcutaneous [SC]) as measured by Groton Maze Learning Test (GMLT) (total number of errors). 	

Subject Population: Healthy male subjects who are native English speakers.
	

Number of Subjects: Part 1: 6 Part 2: Per treatment sequence: 4, total: 40 Estimated Total: 46
	
Number of Sites: Estimated total: 1 site in the United States (US)

Dose Level(s): Part 1: TAK-071 80 mg Scopolamine hydrobromide 0.5 mg Part 2: TAK-071 80 mg and matching placebo. This dose might be adjusted but will not exceed highest well tolerated dose in SRD cohorts or the average maximum observed plasma concentration (C_{max}) and area under the plasma concentration-time curve from 0 to 24 hours (AUC_{24}) seen at no-observed-adverse-effect level (NOAEL) in the 28-day Good Laboratory Practice (GLP) toxicology study in monkeys. Scopolamine hydrobromide 0.5 mg and matching placebo. Donepezil hydrochloride 10 mg and matching placebo.
	
Route of Administration: Part 1: TAK-071, PO; Scopolamine, SC Part 2: TAK-071 and matching placebo, PO Scopolamine and matching placebo, SC Donepezil and matching placebo, PO

Duration of Treatment: Part 1: Single dose Part 2: Single dose in each period; total number of dosing days: 4
	
Period of Evaluation: Part 1: 40 days including Screening Period, Treatment Period, and Follow-up Call/Visit. Part 2: Approximately 21 weeks including the Screening Period, Treatment Periods, and Follow-up Call/Visit.

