6.3 Justification for Study Design, Dose, and Endpoints

6.3.1 Justification for Design for Part 1

An initial substudy (Part 1) has been included since to date TAK-071 has only been administered as a single agent under fasted conditions in Study TAK-071-1001. In the present study, TAK-071 administration will occur 24 hours prior to scopolamine and together with a low-calorie, low-fat breakfast.

Scopolamine has the potential of PK drug-drug interaction as antimuscarinics can inhibit gastrointestinal motility, delay gastric emptying, and prolong gastrointestinal transit time [27,28].

CCI

CCI

6.3.2 Justification for Design for Part 2

This is a randomized, double-blind, sponsor-unblinded, placebo-controlled, 5-treatment, 5-period, 10-sequence crossover phase 1b proof of mechanism study to evaluate the effects of single PO administration of TAK-071, a novel M₁ PAM, on scopolamine-induced deficits in cognitive function in healthy adult male subjects.

The study is being conducted as double-blind and placebo-controlled to avoid subjective bias in the assessment of response. The crossover design was selected to reduce the sample size needed and to minimize intersubject variability.

Scopolamine was selected because it has long been used for the induction of deficits in psychomotor and cognitive function, and the impairments resemble those seen in Alzheimer disease. It is therefore expected that in this study, scopolamine will induce the desired cognitive impairment for the cognitive assessments within a short time with minimal sedation and/or fatigue. To ensure this, pre-enrollment enrichment Screening will be performed for all study subjects who meet Screening inclusion/exclusion criteria after administration of scopolamine 0.5 mg SC. Only subjects who display an acceptable decline in cognitive function with minimal sedation will be allowed to enter the main study.

Donepezil has been selected as the positive control for this study because it is the most frequently used medication for the symptomatic treatment of mild to moderately severe Alzheimer disease at the therapeutic dose of 10 mg once daily (QD).

Combination of donepezil and TAK-071 will provide information about PD effect of an acetylcholinesterase inhibitor in combination with M1PAM measured by amelioration of scopolamine induced cognitive and EEG effects.

CCI

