6.3.3 Justification for Dose

6.3.3.1 *TAK-071*

A high TAK-071 dose will be used in this study to maximize the potential for observing a significant reversal of scopolamine-induced cognitive impairment. The dose of TAK-071 will be selected depending on the results from the FIH Study TAK-071-1001; however, under no circumstances will the selected TAK-071 dose exceed the MTD, or if the MTD is not attained, the highest dose tested in the SRD part of the FIH study. At present, it is planned that the dose for the initial substudy (Part 1) and main study (Part 2) will be 80 mg, this the highest dose tested in an SRD setting to date.

If following a review of the preliminary PK results of Part 1 (initial substudy) reveals that there is an effect of scopolamine and/or food on the plasma exposure of TAK-071 (increase or decrease), the selected TAK-071 dose for Part 2 may be adjusted to ensure that exposures remain on target; and below the lowest no-observed-adverse-effect level (NOAEL) plasma exposure achieved in 4-week GLP animal toxicology studies.

The dosing time of TAK-071 relative to scopolamine will be selected to ensure that both drugs attain their anticipated peak effects at approximately the same time to maximize the potential to observe TAK-071 procognitive effects. Based on preliminary TAK-071 plasma concentration data following a dose of 80 mg indicating that peak concentrations occur at median time of 26 hours postdose, it is planned that dosing of TAK-071 should occur 24 hours prior to scopolamine administration. The precise timing of TAK-071 dosing may be adjusted if warranted based on emerging data.

6.3.3.2 *Donepezil*

Donepezil is the most frequently used medication for the symptomatic treatment of mild to moderately severe Alzheimer disease. Donepezil, administered at the therapeutic dose of 10 mg QD, will serve as a positive control in this study. Donepezil has been previously administered to healthy subjects in the context of multiple phase 1 clinical trials, indicating that single doses of 10 mg are safe and well tolerated in this population [19-22]. In particular, donepezil doses of both 5 and 10 mg have been employed in published [21,22] and unpublished (Study ROF-ALZ_102) scopolamine challenge studies. The higher 10 mg dose is therefore expected to maximize the chances of a successful positive control in the present study.

6.3.3.3 *Scopolamine*

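### The TAK-071 placebo is an empty capsule, so it matches the active capsule in shell size and colour but not in weight or contents

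*Protocol*

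**What the plan says.** Protocol 8.1.1.1 describes TAK-071 as drug substance loaded into a hard gelatin capsule at the site: "The range of TAK-071 drug substance loaded will be 1 to 30 mg per capsule". On the placebo it says: "The matching placebo will be an empty capsule and will also be prepared at the site". Table 8.a agrees. It shows 0 mg of TAK-071 for the placebo, lists no filler for either product, and gives one shell description: "Hard gelatin capsule (Size: 00, Color: Swedish orange opaque)". The same section points to a further document: "Compounding and blinding instructions will be provided to the clinical site using the compounding worksheet or a similar document".

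The other oral drug is handled differently. Table 8.b (section 8.1.1.2) lists "Microcrystalline cellulose, National Formulary", in sufficient quantity, for both the overencapsulated donepezil tablet and its placebo.

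On dose, section 6.3.3.1 states that "it is planned that the dose for the initial substudy (Part 1) and main study (Part 2) will be 80 mg". The Study Summary adds: "This dose might be adjusted but will not exceed highest well tolerated dose in SRD cohorts".

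On blinding, section 6.3.2 gives the purpose: "The study is being conducted as double-blind and placebo-controlled to avoid subjective bias in the assessment of response". Section 8.4 places the randomization schedule with the dispensing pharmacist and keeps subjects, the investigator and all other site staff blinded.

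**The concern.** A placebo protects the blind only as far as it cannot be told from the active product. Here the shells agree, but one holds loose powder and the other holds nothing. An intact capsule can still give a cue through its weight or through powder moving inside it.

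The cue falls on the comparison that matters most. C and B differ only in TAK-071 against its placebo, and so do D and E. TAK-071 is given 24 hours before scopolamine and donepezil 3 hours before, so the TAK-071 capsules are taken on their own, ahead of every post-scopolamine assessment. If a subject or a member of the dosing staff could tell filled from empty, several outcomes would be open to expectation: effort on the GMLT, the self-rated sleepiness score, adverse-event reporting, and the investigator's causality judgement. That is the bias the protocol says blinding is there to avoid.

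**Working it through.** **1. Composition side by side (Tables 8.a and 8.b).**

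| | Active | Placebo |
|---|---|---|
| TAK-071 capsule | 1–30 mg drug substance, no filler | 0 mg, no filler |
| Donepezil capsule | one 10 mg tablet plus cellulose | cellulose |

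The TAK-071 placebo is the only oral product in Part 2 with nothing inside the shell.

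**2. Number of active capsules.** The documents give no count, so there is no stated figure to reproduce. It can be derived as the dose divided by the 30 mg maximum, rounded up.

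- Planned 80 mg: 80 / 30 = 2.67, so at least 3 capsules. With an even split, 80 / 3 = 26.7 mg each.
- Above 30 and up to 60 mg: at least 2 capsules.
- 30 mg or less: at least 1 capsule.

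The minimum of three thus holds only for a dose above 60 mg, and the Part 2 dose may be adjusted.

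**3. Difference in fill.** Active minus placebo is 80 − 0 = 80 mg per dose, or about 27 mg per capsule with three capsules.

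**4. Relative weight.** Shell weight is not in the documents. I assume 90 to 150 mg per shell and three capsules in both arms. The ratio of active to placebo weight is (3 × shell + 80) / (3 × shell).

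| Assumed shell | Active | Placebo | Active heavier by |
|---|---|---|---|
| 90 mg | 350 mg | 270 mg | 30% |
| 120 mg | 440 mg | 360 mg | 22% |
| 150 mg | 530 mg | 450 mg | 18% |

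This range illustrates the size of the cue. It does not show that anyone would detect it.

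**5. Where the cue falls in the design.** TAK-071 is active in C and D (2 periods) and placebo in A, B and E (3 periods). Over a full sequence, each subject would receive filled TAK-071 capsules twice and empty ones three times.

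**6. The one stated figure for C versus B.** Section 13.3 claims 90% power at effect size 0.67 with 26 completers. With a paired t test, the noncentrality is 0.67 × √26 = 3.42 on 25 degrees of freedom, and two-sided power at 0.05 is 90.7%. The figure reproduces, and the capsule point does not touch it.

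**7. What is left under the SAP.** SAP 5.1 marks the primary endpoint as no longer applicable. SAP 7.10.3 neither lists nor summarizes PD endpoints. SAP 7.1 records 12 subjects enrolled in Part 2, none of whom began Period 2. No C versus B result on the GMLT will be reported, and no subject received both kinds of TAK-071 capsule. What remains open to expectation is the Part 2 adverse-event tabulation by treatment (SAP 7.11.1).

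**The case against.** The strongest reply is that the protocol delegates blinding detail to a compounding worksheet outside the documents. Capsule number and handling precautions may be covered there, so those controls cannot be called absent. That stands. It does not rescue the composition, however: the protocol itself fixes the placebo as empty, and a worksheet that added filler would contradict section 8.1.1.1 and Table 8.a.

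Further objections also carry weight:

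- The shell is opaque, so the contents of an intact capsule cannot be seen. This is correct, and it limits the cue to weight, rattle or an opened capsule.
- Handling is not documented. Section 9.2 describes observed dosing with mouth and/or hand checks, but no section says who hands over the capsules, in what container, or whether the investigator who judges causality touches them.
- Donepezil is an imperfect parallel. Its active product is a tablet inside a capsule with backfill, so its placebo needs filler for that reason. The parallel shows that a suitable filler is already in the plan. It does not show that the plan saw a need to fill the TAK-071 placebo.

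A reader might infer more than the documents support:

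- *A mismatch in capsule number, one empty against three filled.* Table 8.a gives composition per capsule, and no section states a placebo count, so no mismatch is shown.
- *That the blind rests entirely on nobody noticing.* The opaque shell, the pharmacist-held schedule and the unseen blinding instructions all count against that.
- *Direct side-by-side comparison by subjects.* Periods are at least 3 weeks apart, so a subject would compare from memory. Staff dosing several subjects could compare more closely, but only under handling arrangements that are not described.
- *A biased primary result.* Under the SAP no such result will be produced.

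**Conclusion.** The point holds as a weakness in the protocol's definition of the placebo. The match is in shell only, and the unmatched feature lies exactly on the contrasts that isolate TAK-071. At the planned dose the gap is 80 mg of fill per dose, which makes the active dose about 18% to 30% heavier if shells weigh 90 to 150 mg and counts are equal. Both of those conditions are assumptions.

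The documents do not show that the cue is detectable, and no size can be put on any bias. No stated figure in the plan is wrong. Early termination narrows the consequence to the design as written, any later use of it, and the descriptive Part 2 adverse-event data. This is therefore a cheap and worthwhile improvement, not a defect that undermines a reported finding. Part 1 is open-label and is unaffected.

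**What to change.** In section 8.1.1.1 and Table 8.a, define the TAK-071 placebo as the same capsule filled with microcrystalline cellulose to the fill weight of the active capsule. State the fill weight by reference to the active capsule, so that it follows any change in the selected dose. Confirm in the same place that the same number of TAK-071 or placebo capsules is given in all five treatments.

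The change leaves the active capsule and the dose as they are. The filler is already in use for the donepezil placebo, and the TAK-071 placebo is already prepared at the site. The edit is to one paragraph, one table and the compounding worksheet, and the running cost is a little more pharmacy time per placebo dose.
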